7.3 Biomarker Plan

List of Biomarker Assays in order of priority use

Priority	Biomarker Name	Assay CLIA?	Use in the Trial and Purpose	Specimens Tested	Collection Time Points	Mandatory or Optional	Assay Laboratory and Lab PI
Biomarkers and correlative studies							
1	Cytosolic K48 ubiquitination	Luminex-based multiplexed sandwich immunoassay for K48 ubiquitination, nuclear CHOP, and cytoplasmic cleaved caspase-3 CLIA: No	Integrated Proof-of-mechanism (measurement of proteasome pathway blockage by assessing the build-up of K48-ubiquitinated proteins in the cytosol)	Tumor biopsy tissue PBMCs	Baseline and cycle 1, day 1, 4-6 hours after treatment (optional at disease progression)	Tumors mandatory for the expansion cohort only (progression biopsy always optional) PBMCs mandatory both	PADIS: [name] [contact]
2	Nuclear CHOP	Luminex-based multiplexed sandwich immunoassay for K48 ubiquitination, nuclear CHOP, and cytoplasmic cleaved caspase-3 CLIA: No	Exploratory Proof-of-mechanism (measurement of the unfolded protein response by assessing the induction of the transcription factor CHOP in the nucleus)	Tumor biopsy tissue PBMCs	Baseline and cycle 1, day 1, 4-6 hours after treatment (optional at disease progression)	Tumors mandatory for the expansion cohort only (progression biopsy always optional) PBMCs mandatory both	PADIS: [name] [contact]
3	Cytosolic Cleaved Caspase-3	Luminex-based multiplexed sandwich immunoassay for K48 ubiquitination, nuclear CHOP, and cytoplasmic cleaved caspase-3 CLIA: No	Exploratory To identify biomarkers of response (measurement of the execution of apoptosis by the accumulation of cleaved caspase-3 in the cytosol)	Tumor biopsy tissue PBMCs	Baseline and cycle 1, day 1, 4-6 hours after treatment (optional at disease progression)	Tumor mandatory for the expansion cohort only (progression biopsy always optional) PBMCs mandatory both	PADIS: [name] [contact]

Priority	Biomarker Name	Assay CLIA?	Use in the Trial and Purpose	Specimens Tested	Collection Time Points	Mandatory or Optional	Assay Laboratory and Lab PI
Biomarkers and correlative studies							
1	Pharmacokinetics	HPLC-MS/MS CLIA: No	Integrated	Blood and urine	Baseline, day 1 (15 min, 30 min, 1hr, 2hr, 4hr, 6hr, 8hr*, 24hr post dose for all patients) and for the first 3 study patients only on cycle 1 day 4 (predose and 15 min, 30 min, 1hr, 2hr, 4hr, 6hr, 8hr*, 24hr post dose)	*All PK collection is mandatory except for the 8-hr post dose.	[name], Alturas Analytics [name]
2	ctDNA	Illumina TSO 500 CLIA: No	Exploratory To evaluate potential associations between CB-5339 activity and genomic alterations	Blood samples	Baseline, cycle 1 day 2, at the start of every cycle, at progression	Optional in escalation, mandatory only in expansion (optional at progression)	MoCha: [name] [contact]

8. STATISTICAL CONSIDERATIONS

8.1 Study Design/Endpoints

The primary objective of this phase 1 study is to establish the safety, tolerability, and recommended phase 2 dose (RP2D) of CB-5339 administered orally on a schedule of once daily, 4 days on and 3 days off, in patients with advanced solid tumors and lymphomas. This study will follow design 3 of the Simon accelerated titration designs (Simon et al., 1997). We will accrue to the next dose level only after we have established safety at lower dose levels. The study will use an accelerated dosing design with doses reflecting one capsule size/dose for patient convenience). Accrual will not proceed to a higher dose level until all patients have been treated at the current dose level, and the last patient treated has been observed for at least one cycle. Intra-patient dose escalation will be permitted; refer to Section 5.2 regarding conditions for permitted intra-patient dose escalation. The MTD dose for CB-5339 is defined as the dose level at which no more than 1 of 6 patients experience a DLT during the first cycle of the treatment, and the dose level below that at which at least 2 (of \leq 6) patients have DLT as a result of the drugs.

8.2 Sample Size/Accrual Rate

There will be 15 patients in the expansion phase, plus 6-18 patients in the dose escalation phase, giving a minimum of 21 patients and a maximum of 33 evaluable patients. To allow for a small number of patients who may not be evaluable, the accrual ceiling for this trial is set at 40 patients.

It is anticipated that 1-2 patients/month may be enrolled onto this trial. It is expected that 22-40 months will be required to accrue the number of patients necessary to complete the trial. This study will enroll a minimum of 5 lymphoma patients; these patients may be in the dose escalation or the expansion cohorts.

PLANNED ENROLLMENT REPORT

Racial Categories	Ethnic Categories				Total	
	Not Hispanic or Latino		Hispanic or Latino			
	Female	Male	Female	Male		
American Indian/ Alaska Native					0	
Asian	3	3			6	
Native Hawaiian or Other Pacific Islander					0	
Black or African American	3	3	1	1	8	
White	9	9	2	2	22	
More Than One Race	1	1	1	1	4	
Total	16	16	4	4	40	

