- To establish the safety, tolerability, and recommended phase 2 dose (RP2D) of CB-5339 administered orally on a schedule of once daily, 4 days on and 3 days off, in patients with advanced solid tumors and lymphomas

Secondary Objectives:

- To evaluate the pharmacokinetic profiles of CB-5339
- To assess the preliminary antitumor activity of CB-5339 in patients with advanced solid tumors and lymphomas
- To determine the effects of CB-5339 on the ubiquitin proteasome system and markers of cell death in pre- and post-treatment tumor biopsies and peripheral blood mononuclear cells (PBMCs)

Exploratory Objectives:

- To evaluate potential associations between CB-5339 activity and genomic alterations assessed in circulating tumor DNA

[figure not shown]
Eligibility:

- Patients \geq 18 years of age must have histologically documented solid tumors whose disease has progressed on standard therapy or for which there is no available standard therapy or therapy known to prolong survival; or aggressive lymphoma who have refused or have no remaining curative options. Patients with indolent lymphomas must have undergone 3 or more prior regimens of therapy

Study Design:

- CB-5339 will be administered orally on a schedule of once daily, 4 days on and 3 days off, in 28-day cycles.
- The trial will follow an accelerated titration design, changing to a traditional 3+3 dose escalation design (3-6 patients per cohort) once specified toxicity criteria are met. A separate 15-patient expansion cohort will further explore pharmacodynamic endpoints and obtain additional pharmacokinetic data at the RP2D.
- Once pharmacodynamic data are available at the RP2D, additional expansion cohorts may be considered to explore pharmacodynamic endpoints at lower dose levels (a protocol amendment will be submitted for these changes to the trial design).
- Blood samples will be obtained for pharmacokinetic and pharmacodynamic analyses and to isolate circulating tumor DNA. Tumor biopsies will be collected at baseline and 4-6 hours after drug administration in the expansion cohort only; an optional biopsy may be collected at disease progression.
- Pharmacodynamic effects of CB-5339 will be assessed through a panel of markers including accumulation of lysine-48 (K48) specific polyubiquitinated substrates in the cytosol, upregulation of transcription factor CHOP in nucleus, and appearance of cleaved caspase-3 in the cytosol.

SCHEMA

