5.2 Definition of Dose-Limiting Toxicity

Determination of dose-limiting toxicity (DLT) will be based on toxicities observed in the first cycle of therapy and felt to be at least possibly related to study drug. A greater than 2-week delay for AEs before cycle 2 would be considered a DLT.

This study will follow design 3 of the Simon accelerated titration designs (Simon et al., 1997). We will accrue to the next dose level only after we have established safety at lower dose levels.

During this accelerated phase, there will be one patient per dose level. After the first instance of a drug-related Grade 2 toxicity (during the first cycle) at any dose level, the accelerated phase will end, and dose escalation will be changed to a 3 + 3 design. All decisions on dose expansion and DLT will be made on the first cycle of treatment.

When the accelerated phase ends, the trial will go back to a traditional 3+3 design. That is, additional patients will be placed on the dose level at which the last new patient was treated; 3 patients will be treated initially at each new dose level.

Number of Patients with DLT at a Given Dose Level	3+3 Escalation Decision Rule
0 out of 3	Enter 3 patients at the next dose level.
≥ 2	Dose escalation will be stopped. This dose level will be declared the maximally administered dose (highest dose administered). Three (3) additional patients will be entered at the next lowest dose level if only 3 patients were treated previously at that dose.
1 out of 3	Enter at least 3 more patients at this dose level. 
• If 0 of these 3 patients experience DLT, proceed to the next dose level.• If 1 or more of this group suffer DLT, then dose escalation is stopped, and this dose is declared the maximally administered dose. Three (3) additional patients will be entered at the next lowest dose level if only 3 patients were treated previously at that dose.
≤ 1 out of 6 at highest dose level below the maximally administered dose	This is generally the recommended phase 2 dose. At least 6 patients must be entered at the recommended phase 2 dose.

If ≥ 2 patients experience DLT on dose level -1, the study will be placed on hold and all data reviewed to make a decision about further evaluation of the study drug.

DLT is defined as an adverse event that is related (possibly, probably, or definitely) to

administration of study drug and fulfills one of the following criteria:

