5.3 Dose Expansion Cohort

Once the RP2D is reached, an additional 15 patients will be treated at this dose to further explore pharmacodynamic endpoints and obtain additional pharmacokinetic data. For the expansion cohort, patients will continue to be monitored for occurrence of toxicities that meet the definition DLT after cycle 1. Once pharmacodynamic data are available, additional expansion cohorts may be considered to explore pharmacodynamic endpoints at lower dose levels (a protocol amendment will be submitted for these changes to the trial design).

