8.3 Analysis of Secondary and Exploratory Endpoints

Once the MTD/RP2D is established, up to 15 additional patients will be enrolled to the expansion phase of the trial. Mandatory tumor biopsies will be obtained in the expansion phase to assess for pharmacodynamic endpoints. With up to 15 patients and a tumor biopsy QA criteria failure rate of 19% with respect to paired (pre- and post-dose) biopsies, we have a 95% likelihood of having at least 10 usable PD paired samples. This will give us at least 90% power to detect a treatment related PD endpoint change of at least 1.8 SDs (with respect to the baseline values of the endpoint) at the 1-sided .01 significance level (to accommodate multiple comparisons).

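### Section 8.2 calls 18 escalation patients and 33 evaluable patients a maximum, but one ordinary cohort expansion under Section 5.2 after an early switch gives 21 and 36

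*Combined protocol and SAP*

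**What the plan says.** Section 8.2 gives 15 patients for expansion "plus 6-18 patients in the dose escalation phase, giving a minimum of 21 patients and a maximum of 33 evaluable patients". It then sets an accrual ceiling of 40, explained as room for a small number of non-evaluable patients. It does not derive 6 or 18.

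The escalation rules are elsewhere:

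- The précis describes a design "changing to a traditional 3+3 dose escalation design (3-6 patients per cohort) once specified toxicity criteria are met".
- Section 5.2 treats one patient per level until the first drug-related Grade 2 toxicity in cycle 1, at whatever level that occurs. From then on each new level starts with three patients.
- After one DLT in three, the Section 5.2 table says "Enter at least 3 more patients at this dose level". If none of the added patients has a DLT, escalation continues.
- After two or more DLTs, "Three (3) additional patients will be entered at the next lowest dose level if only 3 patients were treated previously at that dose".
- For the recommended dose, "At least 6 patients must be entered at the recommended phase 2 dose". Section 8.1 has a matching definition: "The MTD dose for CB-5339 is defined as the dose level at which no more than 1 of 6 patients experience a DLT".

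On the expansion cohort, Section 5.3 says "Once the RP2D is reached, an additional 15 patients will be treated at this dose to further explore pharmacodynamic endpoints", and Sections 7.2.1 and 8.2 also give 15. Section 8.3 says "Once the MTD/RP2D is established, up to 15 additional patients will be enrolled to the expansion phase of the trial".

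**The concern.** A stated maximum should be the largest number the design rules can produce. Here 18 appears to be the count when every level is cleared with exactly three patients. The 3+3 design exists to add patients when a DLT is seen, and the précis itself allows up to six per cohort, so a figure that leaves out every addition cannot bound the escalation phase.

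Two things depend on this. First, the gap between 33 and 40 is presented as the allowance for non-evaluable patients. Escalation patients beyond 18 use the same places. Second, if 40 is reached, the documents do not say clearly what gives way. Sections 5.3, 7.2.1 and 8.2 fix the expansion cohort at 15, while Section 8.3 allows fewer. The pharmacodynamic calculation in Section 8.3 needs all 15.

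**Working it through.** **Inputs.** Six upward dose levels (dose escalation table, Section 5). One patient per level while accelerated and three per level afterwards, with the switch possible at level 1; three more after 1/3 DLT; three more at the next lower level after two or more DLTs if it had only three (all Section 5.2). Expansion of 15, separate from escalation (précis, 5.3, 7.2.1, 8.2). Ceiling 40 (8.2).

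**The plan's own figures.** 15 + 6 = 21 and 15 + 18 = 33, as stated. The ends of the range match 6 × 1 = 6 and 6 × 3 = 18. This origin is inferred.

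**Count with no added patients.** If the switch happens at level *s* and that level is filled to three, escalation through level 6 takes (*s* − 1) + 3 × (7 − *s*) patients. Each addition under Section 5.2 is 3 more.

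| Switch level | No addition | One addition | Trial total (one addition + 15) |
|---|---|---|---|
| 1 | 0 + 18 = 18 | 21 | 36 |
| 2 | 1 + 15 = 16 | 19 | 34 |
| 3 | 2 + 12 = 14 | 17 | 32 |

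**Two explicit paths after a level-1 switch.**

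1. One level has 1/3 and then 0/3 DLTs; the other five have 0/3. Escalation is 5 × 3 + 6 = 21 and the trial 36. This holds even if expansion patients are counted toward the six required at the recommended dose.
2. Levels 1 to 5 have 0/3 and level 6 has two or more DLTs in three. Level 5 must take three more: 3 × 4 + 6 + 3 = 21, and the trial 36. The wording of Sections 5.2 and 8.1 applies here directly, because there is a level with two or more DLTs.

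**A case that depends on reading.** If six patients must be treated at level 6 before expansion opens, a level-1 switch gives 18 + 3 = 21 (36 in all) and a level-2 switch 16 + 3 = 19 (34 in all) with no DLT anywhere. Sections 7.2.1 and 8.3 point that way, but Sections 5.2 and 8.1 word the six-patient rule for a level below one with two or more DLTs. The conclusion does not need this case.

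**Upper end of the rules.** Six levels with six patients each: 6 × 6 = 36 in escalation and 36 + 15 = 51 in all. These become 37 and 52 if three patients, rather than two, are added at the switch level.

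**Room under the ceiling.** 40 − 33 = 7; 40 − 36 = 4; 40 − 39 = 1. After a level-1 switch, three expanded levels give 18 + 9 = 27 in escalation and 42 in all, above the ceiling with every patient evaluable. If six at the recommended dose precede expansion, two expanded lower levels are enough.

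**How likely.** The documents give no toxicity rates, so two profiles are assumed for levels 1 to 6.

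- Profile A: cycle-1 Grade ≥2 in 5, 10, 15, 20, 25, 30%; DLT in 1, 2, 3, 5, 8, 12%.
- Profile B: cycle-1 Grade ≥2 in 10, 20, 30, 40, 50, 60%; DLT in 2, 5, 8, 12, 20, 30%.

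An exact recursion through the rules gives:

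| | A | B |
|---|---|---|
| P(escalation > 18), expansion patients count toward six at level 6 | 0.124 | 0.295 |
| P(escalation > 18), six treated at level 6 first | 0.206 | 0.348 |
| P(escalation > 25, so total > 40), expansion patients count | 0.004 | 0.025 |
| P(escalation > 25), six treated first | 0.009 | 0.035 |

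The recursion also assumes that a lower level with fewer than six patients, including one with only a single patient, is filled to six on step-down; that step-down repeats if that level in turn has two or more DLTs; and that DLTs among patients added at level 6 also trigger it. Without repeated step-down the first row is 0.122 and 0.275. The switch comes at level 1 or 2 with probability 0.05 + 0.95 × 0.10 = 0.145 (A) and 0.10 + 0.90 × 0.20 = 0.28 (B). Given that, with expansion patients counted, P(escalation > 18) is (0.0318 + 0.0585)/0.145 = 0.62 and (0.0698 + 0.1212)/0.28 = 0.68.

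**Usable biopsy pairs (Section 8.3).** With 19% failure, P(at least 10 usable) under Binomial(*n*, 0.81) is 0.951 at *n* = 15, matching the stated 95%. It is 0.891 at 14, 0.777 at 13 and 0.594 at 12.

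**The case against.** The binding number is 40, not 33. The planned enrollment table adds to 40, the upper accrual time of 40 months corresponds to 40 patients at one a month, and a total of 36 fits beneath it. No non-evaluable rate is given, so no shortfall is demonstrated at 36. As a planning range 6 to 18 is reasonable: with expansion patients counted toward the six, mean escalation size is 12.0 under profile A and 15.9 under B, with 88% and 71% of the probability at 18 or fewer. Passing 40 with every patient evaluable is unlikely under either profile, and both profiles are assumptions. The origin of the range is also unproven, since 6 is also the minimum number at the recommended dose. Finally, Section 8.2 might be read as itself capping escalation at 18.

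Most of this stands as a limit on the consequences. It does not rescue the word maximum. Section 8.2 justifies the ceiling by non-evaluable patients and not by escalation overrun. If 18 were a silent cap, Section 5.2 would require patients whom Section 8.2 forbids, with nothing said about which prevails. The counts come from Section 5.2, so they do not depend on where 6 and 18 came from.

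**Conclusion.** The concern holds. The figures 18 and 33 are not maxima under the Section 5.2 rules. One cohort expansion or step-down gives at least 21 and 36 after a level-1 switch, and at least 19 and 34 after a level-2 switch, whichever way the six-patient rule is read. These are counts and need no toxicity assumption; only the probabilities do. The practical effect is moderate: the ceiling is unlikely to be exceeded by evaluable patients alone, but the allowance for non-evaluable patients can shrink from 7 to 4 or fewer, and the expansion cohort is exposed if 40 is reached. The 95% figure in Section 8.3 is correct for 15 patients.

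**What to change.** In Section 8.2, stop describing 18 and 33 as maxima. Either call them planning figures and say that the Section 5.2 rules can lead to 36 or more evaluable patients, or state that 18 is a cap and what happens when it is reached.

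Two related clarifications are worth making in the same amendment, though the main point does not depend on them:

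- Reconcile Sections 5.2, 8.1 and 8.3 on whether the six patients at the recommended dose come before expansion when no level has had two or more DLTs.
- Reconcile the fixed 15 in Sections 5.3, 7.2.1 and 8.2 with the upper limit of 15 in Section 8.3, so that it is clear whether expansion yields at 40. Note in Section 8.3 that the 95% likelihood of ten pairs assumes all 15 are enrolled.

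The cost is wording, mainly in Sections 8.2 and 8.3. Restating the figures adds no patients and changes no dose level, DLT rule or ceiling. The stated upper size of the trial becomes less favourable.

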8.3 Analysis of Secondary and Exploratory Endpoints

Once the MTD/RP2D is established, up to 15 additional patients will be enrolled to the expansion phase of the trial. Mandatory tumor biopsies will be obtained in the expansion phase to assess for pharmacodynamic endpoints. With up to 15 patients and a tumor biopsy QA criteria failure rate of 19% with respect to paired (pre- and post-dose) biopsies, we have a 95% likelihood of having at least 10 usable PD paired samples. This will give us at least 90% power to detect a treatment related PD endpoint change of at least 1.8 SDs (with respect to the baseline values of the endpoint) at the 1-sided .01 significance level (to accommodate multiple comparisons).

8.3.1 Evaluation of Response

All patients included in the study must be assessed for response to treatment, even if there are major protocol treatment deviations or if they are ineligible. Each patient will be assigned one of the following categories: 1) complete response, 2) partial response, 3) stable disease, 4) progressive disease, 5) early death from malignant disease, 6) early death from toxicity, 7) early death because of other cause, or 9) unknown (not assessable, insufficient data).

All of the patients who met the eligibility criteria (with the possible exception of those who received no study medication) should be included in the main analysis of the response rate. Patients in response categories 4-9 should be considered to have a treatment failure (disease progression). Thus, an incorrect treatment schedule or drug administration does not result in exclusion from the analysis of the response rate.

8.3.2 Analysis of Exploratory Endpoints

Exploratory evaluations will be performed, with results reported with appropriate caveats about the exploratory nature of the analysis, and without formal adjustment for multiple comparisons.

9. ADVERSE EVENTS: LIST AND REPORTING REQUIREMENTS

Adverse event (AE) monitoring and reporting is a routine part of every clinical trial. The following list of AEs ([Section 9.1](#)) and the characteristics of an observed AE ([Sections 9.2](#) and [9.3](#)) will determine whether the event requires expedited reporting via the CTEP Adverse Event Reporting System (CTEP-AERS) **in addition** to routine reporting.

9.1 Comprehensive Adverse Events and Potential Risks List (CAEPR)

The Comprehensive Adverse Events and Potential Risks list (CAEPR) provides a single list of reported and/or potential adverse events (AE) associated with an agent using a uniform presentation of events by body system. In addition to the comprehensive list, a subset, the Specific Protocol Exceptions to Expedited Reporting (SPEER), appears in a separate column and is identified with bold and italicized text. This subset of AEs (SPEER) is a list of events that are protocol specific exceptions to expedited reporting to NCI (except as noted below). Refer to the 'CTEP, NCI Guidelines: Adverse Event Reporting Requirements'
http://ctep.cancer.gov/protocolDevelopment/electronic_applications/docs/aeguidelines.pdf for

further clarification.

NOTE: Report AEs on the SPEER ONLY IF they exceed the grade noted in parentheses next to the AE in the SPEER. If this CAEPR is part of a combination protocol using multiple investigational agents and has an AE listed on different SPEERs, use the lower of the grades to determine if expedited reporting is required.

